## APPENDIX II B: STUDY FLOW-CHART

Treatment period

	Baseline		First 6 weeks								Beyond 6 weeks		End of treatment visit	Safety Follow-up visit	Observation 
	≤ 21 days prior to treatment start	≤ 7 days prior to treatment start	D1	D8 (W1) +/- 1 day	D15 (W2) +/- 1 day	D22 (W3) +/- 1 day	D29 (W4) +/- 1 day	D36 (W5) +/- 1 day	D43 (W6) +/- 1 day	Q3 weeks +/- 7 days	Q9 weeks +/- 7 days	Within 7 days after treatment stop	At least 30 days after last study treatment administration (+ 14 days)	Q9 weeks +/- 7 days	
TG4050 Administration 			X	X	X	X	X	X	X	X					
Inclusion/exclusion criteria check	X	X													
Current medical conditions	X														
Physical examination	X		X	X	X	X	X	X	X	X		X	X		
Performance status	X		X	X	X	X	X	X	X	X		X	X		
ECG	X					X			X	X 		X			
AEs/SAEs reporting	X		X	X	X	X	X	X	X	X		X	X		
Concomitant medications	X		X	X	X	X	X	X	X	X		X	X		
CBC		X		X 	X 	X 	X 	X 	X 	X 		X			
Biochemistry		X		X 	X 	X 	X 	X 	X 	X 		X			
Blood samples + cytapheresis for translational research		X 		X 		X 			X 	X 		X 			

	Baseline		First 6 weeks								Beyond 6 weeks		End of treatment visit	Safety Follow-up visit	Observation 	
	≤ 21 days prior to treatment start	≤ 7 days prior to treatment start	D1	D8 (W1) +/- 1 day	D15 (W2) +/- 1 day	D22 (W3) +/- 1 day	D29 (W4) +/- 1 day	D36 (W5) +/- 1 day	D43 (W6) +/- 1 day	Q3 weeks +/- 7 days	Q9 weeks +/- 7 days	Within 7 days after treatment stop	At least 30 days after last study treatment administration (+ 14 days)	Q9 weeks +/- 7 days		
Tumor samples for translational research												X 				
CA-125 concentration		X				X			X	X					X	
Tumor assessment	X 								X		X 				X	

- (1) Blood samples for translational research will be collected at baseline, on CCI [REDACTED], cytapheresis at baseline and on Day 64 or at the end of treatment visit if patient is withdrawn prior to Day 64.
- (2) Tumor samples for translational research will be collected at the time of clinical recurrence
- (3) ECG every 6 weeks up to Day 169, thereafter every 12 weeks
- (4) Imaging to be performed only if the previous imaging has been performed more than 4 weeks before treatment start.
- (5) Tumor assessment by imaging procedures will be performed on Day 43 and every 9 weeks thereafter
- (6) For patients who stopped study treatment before documentation of disease progression
- (7) AEs reported up to 30 days after last treatment, only SAEs related to IMP thereafter
- (8) CBC including RBC, Hb, WBC and differential, platelets & Biochemistry every week up to Week 6, then every 3 weeks up to Month 6 (Day190), thereafter every 12 weeks
- (9) TG4050 will be administered up to a total of 20 injections or until disease progression justifying initiation of further treatment, unacceptable toxicity including occurrence of a dose-limiting toxicity, or patient withdrawal for any reason whichever occurs first.

**LIST OF ABBREVIATIONS**

ABBREVIATIONS	MEANING OF ABBREVIATIONS IN DOCUMENT
AE	Adverse Event
ALP	Alkaline Phosphatase
ALT	Alanine amino-transferase (=SGOT)
AR	Adverse Reaction
AST	Aspartate amino-transferase (=SGPT)
BMI	Body Mass Index
Bpm	Beats per minute
CI	Confidence Interval
CR	Complete Response
CRF	Case Report Form
CTCAE	Common Terminology Criteria for Adverse Events
D	Day
DBP	Diastolic Blood Pressure
DLT	Dose Limiting Toxicity
DNA	Deoxyribonucleic acid
ECG	Electrocardiogram
ECOG	Eastern Cooperative Oncology Group
eCRF	Electronic Case Report Form
EOT	End of Treatment
EOS	End of Study
EPP	Evaluable Per-Protocol Set
FIGO	Federation of Gynecology and Obstetrics
GCIG	Gynecologic Cancer InterGroup
GCP	Good Clinical Practice
HBsAg	Hepatitis B surface Antigen
HCV	Hepatitis C Virus
HGSC	High grade serous carcinoma
ICF	Informed Consent Form
IDMC	Independent Data Monitoring Committee
INT	Integer part
IU	International Unit
LDH	Lactate Dehydrogenase
LLN	Lower Limit of Normal
M	Month
MAX	Maximum
MIN	Minimum

---

MRI	Magnetic Resonance Imaging
MVA	Modified Virus Ankara
N	Number
NA	Not Applicable
NCI	National Cancer Institute
NCS	Not Clinically Significant
PD	Progressive Disease
PFU	Plaque Forming Unit
PP	Per Protocol
PR	Partial Response
PS	Performance Status
PT	Preferred Term
Q1	First quartile
Q3	Third quartile
RBC	Red Blood Cells
RECIST	Response Evaluation Criteria In Solid Tumors
SAE	Serious Adverse Event
SAF	Safety set
SBP	Systolic Blood Pressure
SC	Subcutaneous
sd	Standard deviation
SD	Stable Disease
SI units	International System of units
SOC	System Organ Class
TA	Tumor Assessment
TSAs	Tumor Specific Antigens
TMB	Tumor Mutational Burden
ULN	Upper Limit of Normal
UNK	Unknown
WBC	White Blood Cells
WHO	World Health Organization

---

## 1 UPSTREAM DOCUMENTATION

The following documents were used to prepare the Statistical Analysis Plan:

- TG4050.01 Protocol-HGSC-Version 9.0\_20230912
- TG4050.01\_Bank CRF V8.0\_20241120

## 2 STUDY DESIGN

This study is a multicenter open-label single-arm Phase I evaluating TG4050, an individualized active immunotherapy which refers to a mutanome-directed immunotherapy based on a Modified Virus Ankara (MVA) vaccine specifically designed to target tumor-specific antigens (TSA) identified in each ovarian, fallopian or peritoneal HGSC patient with an asymptomatic relapse.

The study consists of 2 parts for each patient:

### 2.1 Study parts

#### 2.1.1 Screening period

A screening period will start at least 6 months after completion of standard first-line treatment including a platinum-based chemotherapy. Only patients with histological confirmation of serous carcinoma of the ovary, fallopian tube or peritoneum and having high risk cancer defined as high grade and stage IIIC or stage IVA disease, who achieved a complete response after chemotherapy maintained for at least 6 months and from whom tumor tissue is available for tumor neoantigens identification can be included in the screening period.

For those patients, tumor tissue which have been banked at the time of surgery and blood samples will be tested for TSAs identification. TSAs will be used to manufacture an individualized TG4050 mutanome-directed immunotherapy. Manufacturing will take approximately 12 weeks for the vaccine to be prepared in accordance with GMP procedures.

During the screening period, patients will be regularly followed per standard medical practice: serum CA-125 measurements performed in an accredited central laboratory at least every 3 to 4 months and imaging in the event of CA-125 increase and/or clinical symptoms. If a suspicious but indeterminate nodule is identified at study entry, repeat imaging should be obtained 3 months after (+/- 2 weeks) to determine whether the nodule is malignant. Alternatively, a biopsy may be obtained. Patients who have developed an asymptomatic relapse according to the below definitions are eligible for the treatment period. If the patient did not relapse after 2 years of follow-up, this follow-up is performed at least every 6 months (+1 month) according to the investigator's standard practice.

#### 2.1.2 Treatment period

A treatment period with TG4050 monotherapy will start in:

- Cohort A: when patients develop an asymptomatic relapse defined on the basis of progressive serial elevations of serum CA-125 (GCIG criteria) or documentation of low volume radiological disease with CA-125 > ULN. Low volume radiological disease is defined as radiologically visible disease excluding intra-hepatic or intra-splenic metastases, ascites or pleural effusion thought to require drainage.
- Cohort B: when patients develop an asymptomatic relapse with measurable disease excluding intra-hepatic or intra-splenic metastases, ascites or pleural effusion thought to require drainage, whatever serum CA-125 level and for whom further treatment is not planned within 2 months. Longest

diameter on CT-scan must not exceed 2 cm for non-nodal lesions and 2.5 cm in short axis for nodal lesions.

Patients will receive TG4050 up to a total of 20 injections or until documented disease progression as defined by RECIST 1.1 justifying treatment with chemotherapy, or unacceptable toxicity including occurrence of a dose-limiting toxicity, or patient withdrawal for any reason, whichever occurs first.

All treated patients will be followed for:

- Safety assessments performed on a weekly basis for the first 6 weeks and every 3 weeks thereafter.
- Serum CA-125 levels assessed in an accredited central laboratory within 7 days prior to treatment initiation and every 3 weeks after start of study treatment.
- Imaging performed within 21 days prior to treatment initiation, at day 43 and every 9 weeks after study treatment start.
- Immune responses evaluated in the blood at baseline and on days 8, 22, 43, 64, 85 and 211; in the tumor at the time of documented disease progression according to RECIST 1.1.

#### **Safety run-in phase:**

A safety run-in phase will be conducted in the first 3 treated patients from cohort A or B who will be observed during the 6 weeks after TG4050 first dose. During this phase, each patient will be monitored for 4 weeks after the first injection of TG4050 before the next patient can be enrolled.

Enrolment of the next patients will be allowed if none of the 3 patients has experienced a dose-limiting toxicity during the 6 weeks run-in phase:

- any grade  $\geq 3$  toxicity that is at least possibly related to TG4050, with the following exception: pre-existing grade 2 fatigue at baseline that would worsen up to grade 3
- any death

The occurrence of any of those events will trigger a study hold. An evaluation of the cause of toxicity will be performed and corrective measures, if appropriate, will be proposed before recruitment in the study can be reinitiated.

Beyond the safety run-in phase, a dose-limiting toxicity is defined as any treatment-emergent AE  $\geq 3$  toxicity that is at least possibly related to TG4050, with the following exceptions: pre-existing grade 2 fatigue at baseline that would worsen up to grade 3.

In any case, patients experiencing a dose-limiting toxicity will discontinue study treatment permanently.

[figure not shown]
#### **Independent Data Monitoring Committee (IDMC):**

An Independent Data Monitoring Committee will be set up for the purpose of reviewing patients' safety data and the conduct of the study.

The IDMC will review the safety data of the 3 first patients from cohort A or B at the end of the safety run-in phase of the treatment period.

In addition to the review of the first 3 patients, the IDMC will review safety data of all patients included every 3 months during the first year and every 6 months thereafter.

Safety reviews by the IDMC may also be called by Transgene on an *ad hoc* basis upon necessity.

### Graphical study design:

## 2.2 Number of patients

The study will be conducted in France and US and involve 5 centers:

- An approximate number of 60 patients will be included in the screening period

Note: If some patients have not relapsed within 36 months after vaccine manufacture, they will be withdrawn from the study and will not be replaced.

- Cohort A: A least of 13 patients will be enrolled in the treatment period to allow sufficient number of patients evaluable for safety, efficacy and immunological analyses.
- Cohort B: a maximum of 10 patients to be included at the time of full accrual in cohort A.

## 3 STUDY OBJECTIVES AND ENDPOINTS

### 3.1 Primary objectives

The primary objective of the study is to evaluate the safety and tolerability of multiple subcutaneous (SC) injections of a neoantigen-directed active immunotherapy (TG4050) in ovarian, fallopian or peritoneal high grade serous carcinoma (HGSC) patients with asymptomatic relapse.

Particularly adverse events will be assessed throughout the treatment period and graded according to NCI CTCAE version 5.

### 3.2 Secondary objectives

Secondary endpoints are to evaluate the rate of failure to provide TG4050 and failure to treat with TG4050, to evaluate, if applicable, the CA-125 doubling time/time to normalization (this analysis won't be performed given the low number of evaluable patients ) and response according to GCIG criteria and time SAP-template version of 4 Jan 2024

to measurable relapse in cohort A and time to progression in cohort B per RECIST 1.1 and the tumor response according to RECIST 1.1.

### **3.3 Exploratory objectives**

CC1

## **4 STUDY DURATION**

The study started in Q4 2019. The study was stopped due to low inclusion rate in October 2024 with 6 patients treated.

## **5 TREATMENT PLAN**

### **5.1 Randomization**

No randomization is planned in this study.

### **5.2 Duration of Treatment**

TG4050 will be administered up to a total of 20 injections or until disease progression according to RECIST 1.1, unacceptable toxicity including occurrence of a dose-limiting toxicity, or patient withdrawal for any reason whichever occurs first.

## **6 DEFINITION OF THE POPULATIONS TO BE ANALYSED**

### **6.1 Populations**

- Screening period:**

All patients having signed the ICF will be considered as screened patients and included in the screening population (SCR). The percentage of patients not treated afterwards and the corresponding reason, will be analyzed.

Screening population (SCR): all patients who have signed the ICF.

- **Treatment period:**

Safety Analysis Set (SAF): all patients who received at least one dose of TG4050 will be included in the SAF. This is the primary dataset for safety analyses.

Evaluable Safety Set (ESAF): first 3 patients who completed the first 6 weeks of treatment or discontinued before due to the occurrence of a DLT. Patients who are not evaluable for safety analysis during the run-in phase or who are withdrawn for other reasons than toxicity, will be replaced.

Evaluable Per-Protocol Set (EPP): all treated patients without any major protocol deviation who received at least 6 injections of TG4050 corresponding to the treatment induction phase.

[figure not shown]
Modified Evaluable Per-Protocol (mEPP): patients from EPP who are evaluable for immune response meaning at least one pre-dose evaluation and one post-dose evaluation.

Given the small number of patients, this population won't be used.

## 6.2 Major protocol deviations

The identification of major protocol deviations is critical for the EPP definition. A protocol deviation classified as major, will lead to the exclusion of patient from the EPP.

CC1

A non-exhaustive list of protocol deviations including inclusion/exclusion deviations is displayed in APPENDIX 1 – Protocol deviations.

## **7 STATISTICAL DESIGN**

### **7.1 Sample size determination**

No formal sample size calculation is planned for this study.

### **7.2 Data review Meeting**

A data review meeting will occur before the lock for final statistical analysis. Data listings will be produced by project biostatistician before the data review meeting, the list of listings to produce will be defined in agreement with Project Team.

### **7.3 Missing data**

Measurements that were not performed or not recorded will be treated as missing data.

No imputation will be done for missing data, except for calculation of duration with missing and incomplete dates for adverse events (AE) and missing, incomplete date for diagnosis and for concomitant medications. Missing data will be noted as missing in appropriate tables/listings.

Imputation rules for partial date of initial diagnosis:

- If the month and year are present, impute the day by the 15th day of that month.
- If only the year is present, impute by July 1st of that year.

Imputation Rules for Partial or Missing Start Dates for AE:

- If the month and year are present, impute the day by the first day of that month. If the month and year are the same as those of the date of first TG4050 injection, impute the day with the day of first injection.
- If only the year is present, impute by January 1st. If the year is the same as the year of the date of first TG4050 injection, impute by the date of first injection.

Imputation Rules for Partial or Missing Stop Dates for AE:

- If the month and year are present, impute the day by the last day of that month.
- If only the year is present, impute by December 31st of that year. If the stop date is entirely missing, assume the event is ongoing.

As prior and concomitant medications are summarized in two tables according to their start date (before or the day of first administration and after or the day of first administration), partial or missing start date of prior and concomitant medications will be imputed to discriminate them for the two tables. Missing data will be noted as missing in appropriate listings.

Imputation rules for partial or missing start date for CM:

- If the month and year are present, impute the day with the first day of that month.
- If only the year is present, impute by January 1st of that year.

- If the start date is entirely missing:
  - If the end date is after the date of ICF signature, impute the start date by the ICF signature,
  - Or, if the end date is before the ICF signature or missing, impute the start date by the date of birth.

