### **8.6.2.2 Prior and/or Concomitant medications**

Prior and concomitant medications are:

- Medications and/or non-drug therapies taken by the patient prior to start TG4050, continuing or not after the start of the study treatment
- All medications and non-drug therapies taken during the treatment period of the study starting from Day 1 up to 30 days after the last study treatment administration

Prior and concomitant medications will be coded using the WHO Drug Dictionary using latest available including the Anatomical Therapeutic Chemical (ATC) classification and will be listed and summarized by active ingredient by means of frequency counts and percentages.

A table with the frequency and percentage of patients with medications started before D1 ongoing or not at D1 and a second table with the frequency and percentage of patients with Concomitant medications started on or after D1 will be displayed.

The SAF will be used for all above mentioned concomitant medication tables.

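### Partial medication start dates that share Day 1's month or year are imputed to before Day 1, because SAP 7.3 gives medications no check against first injection

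*SAP*

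**What the plan says.** SAP 7.3 gives the purpose of the imputation: "partial or missing start date of prior and concomitant medications will be imputed to discriminate them for the two tables". SAP 8.6.2.2 defines the two tables. The first covers "patients with medications started before D1 ongoing or not at D1"; the other is "a second table with the frequency and percentage of patients with Concomitant medications started on or after D1 will be displayed".

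The medication rules in SAP 7.3 are "If the month and year are present, impute the day with the first day of that month" and "If only the year is present, impute by January 1st of that year". The stop date is consulted only when the start date is entirely missing. The start then becomes the consent date or the date of birth, both of which precede Day 1.

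The AE start-date rules in the same section begin from the same earliest-date default but add a condition. For a missing day: "If the month and year are the same as those of the date of first TG4050 injection", then "impute the day with the day of first injection". For a year alone: "If the year is the same as the year of the date of first TG4050 injection, impute by the date of first injection". The SAP gives no reason for treating medications differently, and no other section of either document supplies the missing condition.

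**The concern.** The rule has one job, to place a drug relative to first injection, and for partial dates it never refers to first injection. It always takes the earliest date compatible with what was recorded. Whenever the recorded month or year also contains Day 1, that earliest date falls before Day 1, except when Day 1 is the 1st of the month or 1 January.

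Two things are at stake. First, protocol 8.2.2.4 has treatment given for an AE recorded on the concomitant medication page. An AE and its treatment recorded with the same partial date can end up on opposite sides of Day 1, so the drug appears to start before the event it treats. Second, SAP 8.6.2.1 uses the medication listings to look for prohibited drugs. A drug begun on treatment could look there like one begun beforehand. Day-missing errors arise only within Day 1's calendar month, so they fall in the early weeks, inside the 6-week DLT observation period.

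**Working it through.** The documents give no figure for this point, so there is none to reproduce.

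**Inputs**
- Split at Day 1: SAP 8.6.2.2. Medication and AE rules: SAP 7.3.
- Window: protocol 3.1 gives six weekly injections, then one every 3 weeks, to 20 in total. Injections 7 to 20 fall on D43 + 21 × (0 to 13), so the last is on D316. Adding the 30 days in SAP 8.6.2.2 gives D346. As a check, the SAP 7.6.2 example gives 6 + int((85 − 1 + 21 − 42)/21) = 9 injections at D85, and D85 is the ninth date in this schedule.
- Assumptions, because the documents give no counts or distribution of partial dates: Day 1 uniform over a 365-day year, true drug start uniform over the window, full 20-injection course.

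**1. Illustrative dates, Day 1 = 10 March 2022**

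| True start | Recorded | Imputed | Placed | Correct? |
|---|---|---|---|---|
| 20 Mar 2022 | Mar 2022 | 1 Mar 2022 | before D1 | no |
| 5 Apr 2022 | Apr 2022 | 1 Apr 2022 | on/after D1 | yes |
| 15 Nov 2022 | 2022 | 1 Jan 2022 | before D1 | no |
| 20 Jan 2023 | 2023 | 1 Jan 2023 | on/after D1 | yes |

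An AE recorded as March 2022 would be imputed to 10 March. A drug recorded as March 2022 would be imputed to 1 March.

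**2. Day missing, start in Day 1's own month.** In a 30-day month with Day 1 on day k there are 31 − k possible on-treatment start days, so the pairs total 30 + 29 + … + 1 = 465. Only k = 1 is placed correctly (30 pairs), so 435/465 = 93.5% are misplaced. Over the year the pairs total 7 × 496 + 4 × 465 + 406 = 5,738, of which 365 are correct. Misplaced: 5,373/5,738 = 93.6%.

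**3. Year only, start in Day 1's own year, within D1-D346.** The pairs number 346 × 347/2 + 19 × 346 = 66,605. Only Day 1 = 1 January is correct (346 pairs). Misplaced: 66,259/66,605 = 99.5%, just under the rounding point (99.48%), so about 99%.

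**4. Share of all on-treatment starts placed before Day 1, by window.** The denominator is 365 × window length. For D1-D346 it is 126,290, giving 5,373/126,290 = 4.3% and 66,259/126,290 = 52.5%. The other windows come from the same enumeration.

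| Window | Day missing | Year only |
|---|---|---|
| D1-D43 | 34% | 94% |
| D1-D190 | 8% | 74% |
| D1-D346 | 4% | 53% |

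Each percentage is a share of starts with that kind of partial date, not of all medication records.

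**5. Under the AE-type rule.** No on-treatment start is placed before Day 1, for either kind of partial date and any window. The reverse error appears. Among drugs truly started in the 30 days before Day 1 (365 × 30 = 10,950 pairs), 5,373 (49%) with the day missing and 10,485 (96%) with the year only move to the on/after-Day-1 side. Both are 0% under the current rule, and both are counted before any stop-date guard.

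**The case against.** The practical reach is small. SAP 8.6.2.2 promises two medication tables, but the output list in SAP section 10 holds none, only Listings 16.2.5.5 (on or after D1) and 16.2.5.6 (before D1). With six treated patients (SAP section 4) these can be read line by line, and SAP 7.3 says missing data will be noted as missing in listings. The before-Day-1 group explicitly includes drugs still ongoing, so a misplaced drug is still reported. Tracking of prohibited drugs is not confined to one side of the split, the AE form records new treatment, and draft outputs are checked for inconsistency. All of this stands and limits the consequence. None of it puts the drug on the right side of Day 1.

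The remedy also exchanges one error for another. Protocol 9.5.4.3 collects medications from the month before treatment, so drugs started shortly before Day 1 are a real group. A stop-date guard rescues only those stopped before Day 1. This stands as a cost. With safety as the primary objective, assigning an ambiguous drug to treatment is the cautious direction and agrees with the SAP's own AE convention.

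Three stronger readings are not supported:
- A reader might infer that any partially dated on-treatment drug is classed as pre-treatment. Later months (day missing) and later years (year only) are placed correctly.
- A reader might take 1 − 1/30.4375 = 96.7% as the share misplaced. That is the chance that Day 1 is not the 1st. An early Day 1 leaves more on-treatment days in the month, so the share misplaced is lower, about 94%.
- A reader might infer that the safety tables contradict one another or that the AE results are biased. AE dates follow their own rule, and no medication table is in the output list.

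**Conclusion.** The defect is real and minor. The medication rule cannot do the sorting it was written for when the partial date shares Day 1's month and year, or its year. The worst cases are near-total misplacement within those subsets (about 94% and 99%); across D1-D346 the figures fall to about 4% for a missing day and 53% for a year alone. These rest on uniform dates and a full course of treatment; patients who stop early would have a shorter window and so a higher share. The number of partial medication dates is not stated, so the count of affected records cannot be estimated, but it is likely to be small. The outputs are descriptive and the primary endpoint, adverse events, is unaffected. What remains is a possible mismatch between an AE and its treatment, and a possible misreading of when a prohibited drug began.

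**What to change.** - Add to the medication rules in SAP 7.3: where the partial start date matches the month and year of first injection (day missing), or its year (year only), impute the date of first injection, unless the stop date is before Day 1.
- Flag imputed start dates in Listings 16.2.5.5 and 16.2.5.6, so that a reader can see which placements rest on the rule. The flag also shows the reverse cases and the entirely missing start dates, which the new condition does not change.
- In the same edit, reconcile the description of the split. SAP 7.3 assigns the day of first administration to both tables, whereas SAP 8.6.2.2 assigns it only to the on-or-after group.

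The cost is about one SAP sentence, one condition in the code and a flag column. The analytical cost is that some ongoing drugs begun shortly before Day 1 will be listed as on-treatment, and the SAP should say that this direction was chosen deliberately.
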